13.4.2 Secondary endpoint

The secondary endpoints fall into two categories for statistical analysis:

- A. Opioid use, subjective pain score, functional assessment of swallow, number of treatment days missed or delayed, and quality of life questionnaire (EORTC QLQ-H&N43 and MDASI-HN) individual items and summary scales.

Each of the endpoint variables in Category A will be analyzed using a Gaussian mixed effects regression model. The model will contain fixed effects for treatment arm and provider and a nested random effect for patient within provider. The mean difference between treatment groups and a 95% confidence interval will be calculated from the model.

- B. G tube required (Y/N)

G tube use will be analyzed using a mixed effects logistic regression model. The model will contain fixed effects for treatment arm and provider and a nested random effect for patient within provider. An odds ratio between treatment groups and a 95% confidence interval will be calculated from the model.

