9 SCHEDULE OF EVENTS

The Schedule of Events table provides an overview of the protocol visits and procedures. Refer to the Study Procedures section of the protocol for detailed information on each assessment required for compliance with the protocol. The Investigator may schedule visits (unplanned visits) in addition to those listed in the Schedule of Events table in order to conduct evaluations or assessments required to protect the wellbeing of the patient. This Schedule of Events will be followed for the entire study.

Short Title: RESILIENCE

Version Date: 18APR2023

Table 4: Schedule of Events

| Examination | Screening ¹ | Pre-Operation ² | Surgery ³ | Post-Operation ⁴ | 5 Weeks Post-Operation | Mid Radiation ⁵ | End of Treatment ⁶ |
|--|------------------------|----------------------------|----------------------|-----------------------------|------------------------|----------------------------|-------------------------------|
| Informed Consent | X | | | | | | |
| Medical History | X | | | | | | |
| Eligibility Criteria | X | | | | | | |
| Vital Signs | X | | | X | | X | X |
| Physical Exam ⁷ | X | | | X | | X | X |
| Karnofsky Performance Status ⁸ | X | X | | X | | X | X |
| Functional Oral Intake Score | X | X | | X | | X | X |
| Hematology ⁹ | X | | | X | | X | X |
| Chemistry ¹⁰ | X | | | X | | X | X |
| Pregnancy Test ¹¹ | | X | | | | | |
| HIV and Hepatitis Serologies ¹² | X | | | | | | |
| Radiation Oncology Consultation | X ¹³ | | | | | | |
| Surgery | | | X ¹⁴ | | | | |
| Celecoxib/placebo ¹⁵ | | | | X | | | |
| Questionnaires ¹⁶ | | X | | X | | X | X |
| Pre-treatment Questionnaire ¹⁷ | | X | | | | | |
| Analgesic Use Record ¹⁸ | | X | | X | | X | X |
| Adverse Events | | | | X | | | |
| Concomitant Medications | X | X | | X | | X | X |
| Telephone Call or Email ¹⁹ | | | | | X | | |

¹ All screening procedures must be completed \leq 28 days prior to surgery.

² This visit may be combined with Screening if all Pre-Operation visit procedures occur \leq 14 days prior to surgery. All pre-operation activities must be completed prior to starting study therapy.

³ All procedures must be completed prior to surgery.

⁴ Post-operation visit will occur 5 to 30 days after surgery.

⁵ Mid-radiation visit will occur 5-35 days after initiation of radiation therapy.

⁶ End of treatment visit will occur 1 to 30 days after the last treatment of radiation.

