⁷ Appendix 8: Treating Investigator Patient Assessment Guidance to be filled out by the treating investigator at the time of physical exam.

⁸ See Appendix 8: Treating Investigator Patient Assessment Guidance

⁹ Hematology to include CBC with platelets and differential.

¹⁰ Chemistry to include a complete metabolic panel (CMP).

¹¹ All women of child-bearing potential must have a negative pregnancy test 7 days prior to surgery.

¹² Only required if there is a known history of HIV, hepatitis B, or hepatitis C to confirm eligibility.

¹³ The radiation oncology consultation should be completed prior to registration if possible. This will include a discussion of the indications for adjuvant radiation treatment, a typical treatment course, and the anticipated/possible side effects so the subjects know what to expect if enrolled on trial.

¹⁴ Prior to surgery, the surgical team (physicians, nursing staff, pharmacy, etc.) will be notified about the patients involvement in the trial to ensure standard of care celecoxib and other prohibited therapies are not inadvertently administered.

¹⁵ Patients will complete 1 to 7 days of study therapy prior to surgery and continue twice daily dosing until the last radiation session.

¹⁶ Appendix 3: MDASI Head and Neck Cancer, Appendix 4: EORTC QLQ-H&N43, Appendix 5: Pain Satisfaction Questionnaire, and Appendix 7: Visual Analog Scale for Pain to be completed within 1 month of the scheduled time-points.

¹⁷ Appendix 6: Pre-treatment Questionnaire to be completed at the pre-operation visit.

¹⁸ Patients will be required to record all opioids taken for pain management on Appendix 4: Pain Management Diary while at home. Diary does not need to be maintained during admission post-surgery but should be started when study therapy is started and continue until completion of study therapy.

¹⁹ 5 weeks (\pm 7 days) post-operation the study team will contact the patient to review their medication diary, adverse events, and analgesic use record. If not returning to the study site at this time point, patients will be asked to fax or scan and email their Patient Dosing Diary and Pain Management Diary use records for the study team for review to ensure timely review of study drug compliance.

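### Section 13.4.2 does not say which visits form the outcome for pain, quality of life and swallowing, and its between-arm model leaves out the pre-dose value that the schedule collects.

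*Combined protocol and SAP*

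**What the plan says.** Section 13.4.2 puts opioid use, pain score, swallowing, missed or delayed radiation days and the two quality-of-life instruments ("individual items and summary scales") into Category A. It then says: "Each of the endpoint variables in Category A will be analyzed using a Gaussian mixed effects regression model". The terms are listed in full: "The model will contain fixed effects for treatment arm and provider and a nested random effect for patient within provider". The output is a single contrast: "The mean difference between treatment groups and a 95% confidence interval will be calculated from the model". There is no visit term, no baseline term and no named visit.

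Table 4 in Section 9 schedules the questionnaires, including the pain scale, at Pre-Operation, Post-Operation, Mid Radiation and End of Treatment. Swallowing is also scored at Screening: "Functional Oral Intake Score | X | X | | X | | X | X". Footnote 2 fixes the timing of the first set: "All pre-operation activities must be completed prior to starting study therapy". Section 10.2 ties the questionnaires at that visit to baseline.

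Sections 1.2, 12.2.2 and 12.2.3 define the measures but name no analysis visit. Section 13.4 promises descriptive statistics by arm for all study variables, which covers the pre-dose values. That is their only stated use.

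**The concern.** A single mean difference from repeated measurements has a meaning only once the contributing visits are fixed. Here two statisticians could follow the text faithfully and fit different data sets: all scheduled rows, or post-dose rows only. The first mixes in visits at which the drug cannot yet have acted. The second is sound, but leaves unused a covariate that patients have already supplied.

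Section 2.1 makes pain control, opioid use, quality of life and function the route by which celecoxib is meant to improve compliance with radiation. In a trial of about 20 patients per arm, the estimates and confidence intervals for these measures are what a later trial would build on. It is therefore worth fixing in advance what they estimate and not giving away precision.

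**Working it through.** The plan states no effect size, SD or power for the secondary endpoints, so there is no figure of its own to reproduce on this point. The 20 per arm comes from Section 13.2. A noncentral-t calculation there (means 72 and 57.2, SD 16.2, two-sided 0.05) gives 80.4% power, matching the stated 80%.

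**Inputs.** From Table 4: one pre-dose and three post-dose visits for pain and quality of life; for swallowing, two pre-dose visits, or one if Screening and Pre-Operation are combined as footnote 2 allows. Assumed, because the documents give nothing: SD 1 at every visit, correlation rp between post-dose visits, correlation rb between baseline and each post-dose visit, 20 per arm, complete data and an effect that is constant after dosing.

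**1. Pre-dose rows entered as outcome.** With complete data and a patient random intercept, the arm coefficient is the difference in patient means. Randomisation makes the expected pre-dose difference zero, so the coefficient is (post-dose visits / all visits) × effect.
- Pain and quality of life: 3/(1+3) = 3/4.
- Swallowing: 3/(2+3) = 3/5 with separate visits, 3/4 with a combined visit.

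A simulation of the Section 13.4.2 model (200 runs, 40 patients, 4 assumed providers, true effect 1.0, correlation 0.5) gave 0.74 and 0.62 for the one- and two-pre-dose layouts. Post-dose rows alone gave 0.99 and 1.02.

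**2. Post-dose rows only, with and without baseline.** The variance factor for a difference between arms is 2/20 = 0.1.
- Without baseline: SE = sqrt(0.1 × (1+2rp)/3).
- With baseline: SE = sqrt(0.1 × ((1+2rp)/3 − rb²)).

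| rp | rb | SE without | SE with | Ratio |
|---|---|---|---|---|
| 0.5 | 0.1 | 0.258 | 0.256 | 1.01 |
| 0.5 | 0.2 | 0.258 | 0.250 | 1.03 |
| 0.5 | 0.3 | 0.258 | 0.240 | 1.08 |
| 0.3 | 0.3 | 0.231 | 0.211 | 1.10 |
| 0.5 | 0.5 | 0.258 | 0.204 | 1.26 |
| 0.7 | 0.7 | 0.283 | 0.176 | 1.61 |

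The first three rows allow for a baseline only weakly related to later visits. The last three assume that all visits are equally correlated.

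**3. Cost of estimating the baseline slope.** With 40 patients, arm and 4 assumed providers, the variance rises on average by a factor c = 1 + 1/33, so the SE rises by sqrt(1.0303) = 1.015, about 1.5%. Dividing the unrounded ratios by 1.015 gives net ratios of 0.99, 1.02 and 1.06 for the first three rows, and 1.08, 1.25 and 1.58 for the last three. Break-even is at rb = sqrt(((1+2rp)/3) × (1 − 1/c)). At rp = 0.5 this is sqrt(0.667 × 0.0294) = 0.14.

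**The case against.** The strongest reply is that a competent analyst would use post-dose visits, since Section 10.2 already treats the Pre-Operation questionnaires as baseline. The 3/4 and 3/5 figures then describe the least natural reading. That is fair. A reader might infer from the patient random effect that the plan intends to pool all visits, but Section 13.4.1 uses the same model wording for a primary endpoint with one value per patient, so the wording proves nothing either way. What stands is that the choice is not written down.

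The second reply is that the gain from adjustment is unknown. Major surgery lies between baseline and every outcome visit, the correlation could be low, and below about 0.14 there is no net gain. This also stands, but it bears only on the baseline term. Naming the outcome visits is needed at any correlation.

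Some stronger readings should be set aside:
- *The baseline is not used at all.* Section 13.4 summarises it descriptively; it is missing only from the between-arm model.
- *The plan may analyse change from baseline.* No section offers a change score.
- *A questionnaire could count as baseline although completed after dosing*, because footnote 16 lets forms be "to be completed within 1 month of the scheduled time-points". Footnote 2 and the 14-day limit in Section 10.2 apply specifically to this visit, and all three can be met together.
- *A pre-dose opioid value exists*, because Table 4 marks "Analgesic Use Record ¹⁸ | | X | | X | | X | X". Footnote 18 and Section 11.4 start the diary with study therapy, and Section 12.2.2 takes opioid use from records kept during it.

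**Conclusion.** The point holds as an omission worth repairing, not as an error in a stated method. For pain, quality of life and swallowing, Section 13.4.2 leaves the outcome visits open and omits an available baseline from the model.

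The size depends on how the gap is filled. Under pooling, a quarter of the effect is lost for pain and quality of life, and between a quarter and two fifths for swallowing, given complete data and a constant post-dose effect. Under post-dose analysis without baseline there is no dilution, and the loss of precision ranges from negligible to substantial across correlations that are all assumed.

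A reader might infer that the trial's main conclusion is at risk. It is not: the primary endpoint has no pre-dose counterpart, and neither its analysis nor the sample size is touched. The secondary results are planned as estimates with confidence intervals in a pilot, so this is an inexpensive improvement of moderate value.

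**What to change.** In Section 13.4.2, for the pain scale, the quality-of-life scales and swallowing:
- Define the outcome as the Post-Operation, Mid Radiation and End of Treatment values only.
- Fit fixed effects for arm, provider, visit and the last pre-dose value, with a patient random intercept.
- Report the arm difference averaged over the post-dose visits with its 95% confidence interval. Add visit-specific differences for scales as descriptive output, because post-surgical and radiation-phase symptoms may differ.
- State how a missing pre-dose value is handled.

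Opioid use and missed radiation days take no baseline term: the diary starts with study therapy, and missed days have no pre-dose counterpart.

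The cost is a paragraph of SAP text and a few lines of code; no visit or assessment is added. The downsides are about 1.5% in SE for the slope, no net gain if the baseline correlation is below about 0.14, the extra rule for missing baselines and somewhat more output. The wording should be settled before treatment assignments are disclosed for analysis.

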11.1 Physical Examinations and Vital Signs

Patients will have physical examinations to include major body systems, vital signs, assessment of Karnofsky performance status (see Appendix 8), Functional Oral Intake Score (Table 5), weight and height (height will be measured at screening only) at the time points described in the Schedule of Events. If necessary to facilitate scheduling, physical exam may occur one day prior to study treatment. Appendix 8: Treating Investigator Patient Assessment Guidance is to be filled out by the treating investigator at every physical exam.

Vital signs, to include blood pressure, pulse rate, and temperature will be also recorded at the time points described in the Schedule of Events.

Table 5: Functional Oral Intake Scale

| Score | Performance | Implication | Deficit |
|--------------|--------------------|---------------------------------|----------------|
| 1 | Aspirates saliva | Nothing by mouth | Profound |
| 2 | Tube dependent | Nothing by mouth/minimal trials | Profound |
| 3 | Tube dependent | Full trials by mouth | Severe |
| 4 | Total Oral | Single texture trials | Moderate |
| 5 | Total Oral | Multiple texture trials | Mild |
| 6 | Total Oral | By mouth/ restrictions | Minimal |
| 7 | Regular diet | By mouth/ no restrictions | Normal |

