12.2.3 Functional Outcome

Functional outcomes will be compared between Arm 1 and Arm 2. Activity level will be assessed utilizing Karnofsky Performance Status and the use of G tube (yes or no) will be noted at every study visit. Patient-reported quality of life will be assessed by QLQ-H&N43 as indicated in the Schedule of Events. Swallowing capabilities, including food and liquid variety, will be captured through the use of a 7-point, Functional Oral Intake Scale as assessed by the treating investigator.

The number of days of adjuvant radiation missed or delayed will be retrospectively collected and compared between Arm 1 and Arm 2. Every day that treatment is delayed will be counted until the resumption of therapy.

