Appendix 8: Treating Investigator Patient Assessment Guidance

3. Does the patient use a feeding tube?

Yes No

Investigator Signature

Date

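### The G tube model in Section 13.4.2 B leaves the Screening feeding-tube status unused and does not separate tubes present before dosing from tubes needed afterwards

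*Combined protocol and SAP*

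**What the plan says.** **Analysis.** Section 13.4.2 lists G tube use, as a yes/no variable for a tube being *required*, as the only Category B endpoint. It states that "G tube use will be analyzed using a mixed effects logistic regression model". The terms are fixed: "The model will contain fixed effects for treatment arm and provider and a nested random effect for patient within provider". So is the output: "An odds ratio between treatment groups and a 95% confidence interval will be calculated from the model". No p-value is planned here, unlike for the primary endpoint in 13.4.1. The section does not define *required*, name the visits analysed, include a visit term or a baseline term, or restrict the analysis to patients without a tube.

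**Data collection.** Section 12.2.3 says that "the use of G tube (yes or no) will be noted at every study visit". Section 11.1 says that "Appendix 8: Treating Investigator Patient Assessment Guidance is to be filled out by the treating investigator at every physical exam". Item 3 of that form asks "Does the patient use a feeding tube". Table 4 schedules physical exams at Screening, Post-Operation, Mid Radiation and End of Treatment, so one of the four scheduled records precedes the first dose.

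**Population and allocation.** Section 5.1 admits recurrent as well as primary disease, and nothing in Section 5 excludes a patient who already has a tube. Section 7.1 allows dosing by mouth or by tube throughout, including the days before surgery. Sections 4.2 and 6 stratify randomisation by treating provider only.

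**The concern.** A tube in place before the first dose cannot reflect an effect of the study drug. Under the model as written, a patient whose early tube stays in use can score the same as one who first needs a tube after surgery or during radiation. If all visits enter the model, the Screening record itself becomes an outcome row, with no visit term to set it apart.

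Earlier tube status is likely to predict later tube status strongly, and it is already on the form. Leaving it out has two possible costs. Patients whose outcome is settled before dosing shrink the contrast between arms. In a trial of about 40 evaluable patients, an uneven split of such patients also moves the estimate by chance. What is at stake is the tube component of the functional secondary objective.

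**Working it through.** **1. Number of patients.** The documents give no tube rate, odds ratio or power for this endpoint. The only design figure that fixes its size is the primary calculation in 13.2: means 72 and 57.2, SD 16.2, 20 per arm, two-sided alpha 0.05. The difference is 72 − 57.2 = 14.8, and the noncentral t power is 80.4%, which agrees with the stated 80%. I therefore use 20 per arm. All tube rates below are assumptions.

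**2. Dilution.** Let *b* be the share with a tube at Screening, all still in use later and scored yes. Let *p* be the rate of later tube use among patients tube-free at Screening. The analysed rate in an arm is *b* + (1 − *b*) × *p*. Assume *p* = 50% on placebo and 25% on celecoxib, an odds ratio (OR) of (0.25/0.75)/(0.50/0.50) = 0.33.

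| *b* | Placebo rate | Celecoxib rate | OR | Difference (points) |
|---|---|---|---|---|
| 0% | 0.500 | 0.250 | 0.33 | 25.0 |
| 10% | 0.550 | 0.325 | 0.39 | 22.5 |
| 20% | 0.600 | 0.400 | 0.44 | 20.0 |
| 30% | 0.650 | 0.475 | 0.49 | 17.5 |

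For example, at 20%: (0.40/0.60)/(0.60/0.40) = 0.44. The risk difference shrinks too, so this is not merely a property of odds ratios. With other assumed rates at *b* = 20%, 60% vs 30% moves the OR from 0.29 to 0.37, and 40% vs 20% moves it from 0.38 to 0.52.

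**3. Chance imbalance.** At 20% Screening prevalence, the between-arm difference in that share has SD √(2 × 0.2 × 0.8/20) = 0.126, so gaps up to about 25 points are within chance. By the exact binomial, the arms differ by 4 or more such patients in 16% of randomisations and by 5 or more in 7%. Take no drug effect, 40% later tube use in both arms, and a split of 2/20 placebo vs 6/20 celecoxib. The rates are 0.1 + 0.9 × 0.4 = 0.46 and 0.3 + 0.7 × 0.4 = 0.58, so the expected OR is (0.58/0.42)/(0.46/0.54) = 1.62. The reverse split gives 0.62.

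**4. Power with and without adjustment.** Simulation with 20 per arm, one post-treatment record per patient, 95% persistence of an early tube, provider effects omitted, and a likelihood-ratio test for arm. Entries are power without → with Screening status in the model.

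| Later tube use, placebo vs celecoxib | 10% at Screening | 20% | 30% |
|---|---|---|---|
| 60% vs 20% (1,000 trials per setting) | 61% → 74% | 49% → 64% | 45% → 60% |
| 50% vs 25% (2,000 trials per setting) | 29% → 37% | 21% → 32% | 19% → 28% |

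The gain is about 13 to 16 points in the first row and about 8 to 11 in the second. It is about 4 to 10 points at 40% vs 20%, and 4 to 5 at 60% vs 40%. With no drug effect, the adjusted test rejects in about 3 to 7% of trials, so the gain is not mainly an inflated error rate. If no patient has a tube at Screening, the gain is zero.

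**The case against.** **Are early tubes expected?** A reader might infer so from the tube-dosing option in 7.1. The section does not support that. It states one route rule for the whole course, and the option would be needed after surgery in any case. Pre-surgical tubes are permitted, not documented. Karnofsky of at least 70 and albumin above 3.5 g/dL do not exclude tube users, but they lend no support to a prevalence of 20 to 30%. This objection stands and limits the size of the point.

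**Do pre-existing tubes certainly count as events?** A reader might infer this as well. The text leaves it open: *required* could mean in use at a visit, ever in use, or newly needed. Under the last meaning the miscount disappears. No section adopts it, so the wording still needs settling.

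**Is the odds ratio biased?** It is not. Under randomisation an imbalance in early tubes is chance, and the confidence interval reflects it. The unadjusted OR is a valid comparison of on-study tube use. The adjusted OR is conditional on Screening status and is a different quantity.

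**Is power the right measure?** Only an OR and interval are planned. Power serves here as a proxy for precision. The largest gains rest on 60% vs 20%, a very large assumed effect; in the smaller-effect settings power is poor either way, below about 37%.

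**Is it handled elsewhere?** Section 13.4 promises descriptive statistics by arm for all study variables, so an imbalance at Screening would be visible. It would not be adjusted for. Category A uses the same terms without a baseline value, so the choice is general. The G tube case differs because early status also affects what counts as an event.

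**Conclusion.** The point holds as a low-severity improvement. The Category B model omits a strong candidate predictor that is already collected before dosing, does not name its outcome visits, and does not separate earlier tubes from later ones.

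If some patients have a tube at Screening, keep it and are scored yes, an assumed OR of 0.33 is reported as about 0.39 to 0.49 at 10 to 30% prevalence. Adjustment then gains about 4 to 16 points of power with 20 per arm, depending on the assumed effect and prevalence. All of this rests on assumed tube rates, and the benefit is nil if nobody has a tube at Screening. The documents do not support calling it a systematic bias or treating the miscount as certain. The primary analysis is untouched.

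**What to change.** Amend Section 13.4.2 B to:

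- use only post-dose visits as outcomes, name them, and add a visit term if more than one is used;
- say what *required* means, and whether the any-feeding-tube item in Appendix 8 is the source for the G tube endpoint;
- add Screening feeding-tube status (Appendix 8, item 3) as a fixed covariate, with a penalised (Firth-type) fit if the data separate, for instance because every early tube persists;
- state that the adjusted odds ratio is conditional on Screening status and so differs from the unadjusted one;
- report, by arm, the proportion of patients tube-free at Screening who later need a tube.

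The cost is wording, with no new data, visits or patients. The downside is one more parameter in a small model, and patients with a tube at Screening will add little information. Making the change before unblinding avoids a later switch that would look post hoc.
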